1. SYNOPSIS

Long Study Title	An Investigation into the Efficacy of Online Cognitive Behaviour Therapy for Insomnia (“Sleepio”) for Stroke Survivors	
Short Study Title (to be used on participant-facing documents, if applicable)	Improving sleep in rehabilitation after stroke (INSPIRES)	
Nature of Study Participants	Stroke survivors	
Intended number of participants	86	
Design	Randomised controlled	
Location	In the participant's home / online	
	Objectives	Outcome Measures
Primary	The primary objective of this study is to assess whether self-reported sleep quality in stroke survivors is improved following online Cognitive Behavioural Therapy for Insomnia (“Sleepio” programme).	The primary outcome measures for this study will be the change in Sleep Condition Indicator score following completion of the programme.
Secondary	
The secondary objectives are to assess changes in measures of sleep quality and self-reported measures of quality of life and anxiety following the intervention and at 8 week follow up.
 
To assess the cost-effectiveness of online CBT-I in stroke survivors when compared to a brochure of sleep hygiene information.
	
Changes in sleep fragmentation and wake after sleep onset, assessed with actigraphy, sleep onset latency assessed through the sleep diaries, anxiety and depression using the PHQ9 and GAD7, quality of life using the Stroke impact scale-8 and Euroqol-5 Dimensions- 5 Levels (EQ-5D-5L)
 
Changes in healthcare costs during the 8-week follow up.

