5.5. Baseline Assessments

After the signed consent form has been received by the researchers, the participant will be sent the GAD-7, PHQ-9, SCI, Stroke Impact Scale-8, Stroke Efficacy questionnaire and EQ-5D-5L to complete. Participants will also receive a questionnaire asking them to recall over the last 8 weeks all the contacts they have had with the healthcare service. This will be a modified version of the Client Service Receipt Inventory (CSRI).

We will also ask them to wear an actigraphy monitor on their wrist for one week and to complete a sleep diary at the same time. We will provide them with a prepaid envelope to send the materials back.

We will also record demographic variables including; age, sex, partner status, whether they share a bed, medications, employment status and date of stroke.

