5.6. Subsequent Assessments

Participants randomised to the intervention group will receive access, via web link and activation code to the digital CBT-I programme “Sleepio”. This programme will require the participant to keep a daily sleep diary and engage in weekly sessions comprising weekly CBT-I content. Participants randomised to the control group will be given access to an online sleep diary to complete for one week. They will also receive a brochure with sleep hygiene information and then will be asked to complete the online sleep diary again 8 weeks later.

During the trial, participants will be asked to keep a record, in a specially designed log book, of their contacts with the healthcare service.

Upon completion of the programme, participants will once again be sent questionnaires to complete (PHQ-9, GAD-7, SIS-8, Stroke Efficacy questionnaire and EQ-5D-5L), in addition to the wrist worn actigraphy monitor and the sleep diary to use for one week.

At 8 weeks follow up, all assessments conducted as baseline will be repeated and the intervention group will complete a debriefing feedback questionnaire.

6. Feasibility and Adverse events

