8. STATISTICS AND ANALYSIS

8.1. Description of Statistical Methods

The efficacy of Sleepio will be assessed by comparing the SCI scores of the intervention and control groups from baseline to immediately post-intervention, following an intention to treat analysis approach. Changes in the primary outcome measure from baseline to post-intervention will be assessed with analysis of variance (ANOVA) (or linear mixed model or non-parametric equivalents if necessary) with inclusion of baseline score as a covariate.

Secondary outcomes will be assessed with ANOVA (or linear mixed model or non-parametric equivalents if necessary). EQ-5D-5L responses will be converted into utility values using population preferences (van Hout et al., 2012) and combined with survival information to calculate Quality Adjusted Life-Years (QALYs). All resource use will be valued using 2018/19 unit costs obtained from healthcare compendiums, (Curtis and Burns 2018) NHS reference costs, (<https://improvement.nhs.uk/resources/reference-costs/>) and British National Formulary (<https://www.bnf.org/>). Costs of CBT-I will be obtained from the trial.

An incremental analysis will be performed, assessing the differences in costs between the two interventions and dividing by the difference in QALYs gained in order to generate an incremental cost-effectiveness ratio (ICER). ICERs will be estimated using an NHS perspective. The 10 000 bootstrapped pairs of incremental costs and incremental QALYs will be plotted on cost-effectiveness planes to display the uncertainty in the estimated ICER. Cost-effectiveness acceptability curves (CEACs) will be derived to display the probability of the CBT treatment being cost-effective, as the ceiling ratio for the maximum acceptable cost-effectiveness ratio varies from £0 to £85 000 per QALY gained.

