8.2. The Number of Participants

68 full datasets (1:1 ratio intervention to control) are intended to be collected for this study. This is based on a power calculation using the between groups effect size estimate ($d=1.2$) from a previous study of digital CBT-I in people with insomnia (Espie et al., 2012). This would therefore require 24 participants in total to find an effect. However, we wish to also include people with sleep disturbance who do not meet the criteria for insomnia. Based on our open-label feasibility study for digital CBT-I in this population (Smejka et al., 2022) we anticipate that 50% of participants will not meet the criteria for insomnia, and based on that study we would anticipate a more modest effect size ($d=0.7$), which would require 68 participants (assuming $\alpha=0.05$ and power of 80%). Allowing for approximately 25% drop out, we therefore aim to recruit 86 participants in total. This should allow us to do a subgroup analysis including only people who meet the criteria for insomnia, as well as a full group analysis.

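### The PHQ-9 total contains a sleep item and a tiredness item, so part of any difference in the depression outcome may be better sleep; a pre-specified score without them is a cheap safeguard

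*Combined protocol and SAP*

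**What the plan says.** The intervention is aimed at sleep. The primary objective in the synopsis is "to assess whether self-reported sleep quality in stroke survivors is improved following online Cognitive Behavioural Therapy for Insomnia", measured by the Sleep Condition Indicator (SCI). Among the secondary outcome measures the synopsis lists "anxiety and depression using the PHQ9 and GAD7".

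The whole questionnaire is administered. In section 5.5, "the participant will be sent the GAD-7, PHQ-9, SCI, Stroke Impact Scale-8, Stroke Efficacy questionnaire and EQ-5D-5L to complete". In section 5.6, after the programme, "participants will once again be sent questionnaires to complete (PHQ-9, GAD-7, SIS-8, Stroke Efficacy questionnaire and EQ-5D-5L"). The baseline assessments are then repeated at the 8-week follow-up.

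For analysis, section 8.1 has one sentence covering these outcomes: "Secondary outcomes will be assessed with ANOVA (or linear mixed model or non-parametric equivalents if necessary"). It names no modified PHQ-9 score, no item-level analysis and no caution about interpretation.

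The worded secondary objective covers sleep quality and "self-reported measures of quality of life and anxiety following the intervention and at 8 week follow up". Depression is not named there. It appears only in the outcome-measures column.

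**The concern.** If Sleepio improves sleep, the PHQ-9 sleep item should improve with it, and the tiredness item may as well. Both count towards the total. The difference between arms in the total then mixes two things: any change in mood, and a second count of the effect already measured by the SCI. As written, the plan gives the reader no way to tell them apart.

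Less depression after stroke is a different clinical claim from better sleep. An estimate that blends the two will overstate the first whenever the treatment achieves the second. A score without those items is also more convincing if named in advance than if chosen after the results are known.

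**Working it through.** **The plan's own figure.** Section 8.2 says "we would anticipate a more modest effect size ($d=0.7$), which would require 68 participants", "assuming $\alpha=0.05$ and power of 80"%. A two-sided two-sample t-test at d=0.7, alpha 0.05 and 80% power gives 68 in total, 34 per arm, so the figure reproduces (achieved power 81.2%). The plan states no figure for the PHQ-9. I use only the 34 per arm and the d=0.7 from this section.

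**Assumptions not in the documents.**
- Item content: nine items scored 0 to 3 (total 0 to 27), one on sleep and one on tiredness. The sponsor can confirm this on its own form.
- Item SD 0.9 to 1.1; total SD 5 to 6.
- The sleep item moves by d=0.7. The plan sets that value for its main comparison, not for a PHQ-9 item.
- In the larger case the tiredness item moves half as much (0.35 SD). In the smaller case it does not move.
- No other item moves, so the result isolates the overlap.

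**Share of the score.** Sleep item: 3/27 = 11%. Sleep and tiredness: 6/27 = 22%.

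**Size of the overlap.** Shift in points = standardised item shift × item SD, summed over the items that move. Standardised difference on the total = shift / total SD.

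| Case | Shift in points | d, smallest | d, largest |
|---|---|---|---|
| Sleep item only | 0.7×0.9 = 0.63 to 0.7×1.1 = 0.77 | 0.63/6 = 0.105 | 0.77/5 = 0.154 |
| Sleep, plus tiredness at half | 1.05×0.9 = 0.945 to 1.05×1.1 = 1.155 | 0.945/6 = 0.158 | 1.155/5 = 0.231 |

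**Would the overlap alone be significant?** Two-sided t-test, alpha 0.05, 34 per arm:
- d=0.105: 7.1%
- d=0.154: 9.6%
- d=0.158: 9.8%
- d=0.231: 15.5%

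So the chance is about 7% to 16%, against 5% with no shift at all. Section 8.1 names a baseline covariate only for the primary outcome. If one were also used here, with an assumed correlation of 0.6, d is divided by √(1−0.36) = 0.8 and the range becomes about 8% to 22%.

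**Effect on the estimate.** Suppose, for illustration, that the other items produce a real difference of d=0.30 on the total. Adding the overlap gives 0.30+0.105 = 0.405 to 0.30+0.231 = 0.531. The estimate is then larger by 0.105/0.30 = 35% to 0.231/0.30 = 77%. The chance of significance at 34 per arm rises from 23% to between 38% and 58%.

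**The case against.** Four points can fairly be made for the plan as it stands.

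- **The standard total is a recognised depression outcome.** Disturbed sleep and fatigue can be part of depression, so removing those items may discard real signal. This stands. It is why the total should remain the secondary outcome and the shortened scores should be sensitivity analyses.
- **The overlap is small.** On the assumptions above it would usually not be significant alone, and detecting d=0.23 with 80% power would take about 600 participants. This also stands. What remains is inflation of the estimate, which does not depend on significance.
- **The inputs are assumed.** The documents give neither SDs nor item content, and applying d=0.7 to a single item is a further step. This limits the precision of the range. It does not remove the overlap, since the item content is fixed by the instrument that the protocol names.
- **The score can be derived later from data already held.** True, but a later choice would carry less weight.

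A reader might go further and infer that the treatment will lower the PHQ-9 with no change in mood, and that the trial would report this as a depression benefit. The documents support neither step. Overlap allows part of a fall to come from sleep; it does not show that mood is unchanged, and it arises only if sleep improves. No section sets a reporting rule or plans a depression claim, and the worded secondary objective names anxiety, not depression.

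**Conclusion.** The point holds as a cheap improvement to one secondary outcome. Under the plan as written, a PHQ-9 difference could not be separated from improved sleep. The overlap is about 0.6 to 1.2 points (d about 0.10 to 0.23), conditional on the assumed SDs, on the planned d=0.7 carrying over to the sleep item and, at the upper end, on tiredness moving half as much. This is too small to produce a significant result by itself in most trials of this size, but large enough to inflate a modest real effect noticeably. The primary SCI analysis and the sample size are not affected.

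**What to change.** In the synopsis and section 8.1, before any outcome data are seen by arm:

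1. Keep the PHQ-9 total as the secondary depression outcome.
2. Pre-specify two sensitivity analyses with the same model: the total without the sleep item (eight items, 0 to 24), and the total without the sleep and tiredness items (seven items, 0 to 21). Report both beside the total, with confidence intervals.
3. State that a depression benefit separate from better sleep will be claimed only if the result without the sleep item is consistent with it.
4. Say what consistent means. A shorter score gives a smaller raw difference even when every item moves equally (8/9 = 89% and 7/9 = 78% of the full difference), so a comparison of standardised or per-item differences is fairer than one of raw points. A requirement that each score be significant would be too strict at this sample size.

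The cost is two derived scores from data already collected, with no added visits, questionnaires or participants. The downside is that shortened scores are less comparable with published cut-offs and may drop some genuine depression signal, which is why the full total is still reported.

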3. STUDY DESIGN

The study will be a single-blinded randomised controlled trial involving the completion of a six-week digital CBT-I programme. Following written informed consent, participants will be posted baseline questionnaires to complete and an actigraphy monitor to record objective sleep measures for one week. After this, participants will be randomised to CBT-I or control using an online randomisation software (rando.la) with minimisation of between group differences based on age and baseline self-reported sleep quality (Sleep Condition Indicator (SCI) score). The control group will be given access to an online sleep diary to complete daily for one week. They will also be given a brochure containing sleep hygiene information. 8 weeks later they will be asked to complete the online sleep diary again for one week.

Participants allocated to Sleepio will complete daily online sleep diaries for the duration of the study and will receive weekly online CBT-I sessions as part of the programme. Both groups will complete their programmes at home.

Participants will be sent the questionnaires and actigraphy monitor again to be worn for another week immediately following completion of the programme (Sleepio) or following the 6-week sleep diary (control) and at 8 weeks follow up. At 8 weeks follow up, participants in the intervention group will also be sent a debriefing questionnaire to get feedback on the programme and the research study.

Participants allocated to the control group will be sent a web link and activation code for the Sleepio programme following completion of the 8 week follow up.

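### The synopsis limits the cost outcome to the 8-week follow-up, which conflicts with the log book, Section 8.1 and the EQ-5D-5L schedule, and no common period for costs and QALYs is stated

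*Combined protocol and SAP*

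**What the plan says.** Cost-effectiveness is a secondary objective in the synopsis: "To assess the cost-effectiveness of online CBT-I in stroke survivors when compared to a brochure of sleep hygiene information". The outcome listed for it is "Changes in healthcare costs during the 8-week follow up". The synopsis names no other cost outcome.

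The procedures describe two sources of resource-use data:

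- **Modified CSRI (Section 5.5).** At baseline participants are asked to "recall over the last 8 weeks all the contacts they have had with the healthcare service". Section 5.6 repeats all baseline assessments at the 8-week follow-up, so the CSRI returns then. It is not in the list of questionnaires sent when the programme ends.
- **Log book (Section 5.6).** "During the trial, participants will be asked to keep a record, in a specially designed log book, of their contacts with the healthcare service". This is not confined to follow-up.

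EQ-5D-5L is collected at baseline (Section 5.5: "Stroke Impact Scale-8, Stroke Efficacy questionnaire and EQ-5D-5L to complete"), after the programme and at follow-up (Section 5.6).

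Section 8.1 gives unit-cost sources for all resource use, says that the CBT-I cost will come from the trial, and defines the ICER as "assessing the differences in costs between the two interventions and dividing by the difference in QALYs gained". It states no start, end or time horizon for either quantity.

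**The concern.** An ICER is interpretable only if costs and QALYs are accumulated over the same period. The synopsis confines costs to follow-up, and the CSRI timing fits that restriction: an 8-week recall before baseline and another ending at follow-up. An analyst who followed the synopsis would leave out healthcare contacts in the weeks when Sleepio is being delivered. The utility data nevertheless start at baseline, and the comparison is of the whole intervention with the brochure.

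The ICER, the bootstrapped cost-effectiveness plane and the acceptability curves up to £85 000 per QALY all rest on this choice. CSRI data for the programme weeks would also be hard to recover once participants have finished.

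**Working it through.** The plan gives no cost, QALY or ICER figure to reproduce. The check is therefore a comparison of windows, followed by simple arithmetic.

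**Windows as written**

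| Item | Place | Period covered |
|---|---|---|
| Named cost outcome | Synopsis | 8-week follow-up |
| CSRI | 5.5, 5.6 | 8 weeks before baseline; 8 weeks before the follow-up visit |
| Log book | 5.6 | Whole trial |
| CBT-I cost | 8.1 | Arises in the programme weeks |
| EQ-5D-5L | 5.5, 5.6 | Baseline, post-programme, follow-up |
| QALY window, ICER horizon | 8.1 | Not stated |

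**Length of the gap.** The design is "completion of a six-week digital CBT-I programme" (Section 3), with repeat assessments "immediately following completion of the programme (Sleepio) or following the 6-week sleep diary (control) and at 8 weeks follow up". If follow-up starts at programme end:

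- Total period = 6 + 8 = 14 weeks.
- Share covered by the synopsis outcome = 8/14 = 57%.
- Share omitted = 6/14 = 43%.

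If the post-programme assessment falls at 7 or 8 weeks (my assumption, for slow completers), the omitted share is 7/15 = 47% or 8/16 = 50%.

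The start of follow-up is not explicit, since the control diary is repeated 8 weeks after the first diary week. If the 8 weeks ran from randomisation, the gap would vanish. However, follow-up would then come only 8 − 6 = 2 weeks after programme end, and the synopsis and Section 3 list the two assessments as distinct. Programme end is the likelier origin.

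**What the omission does to costs.** Let δ be the between-arm difference in healthcare cost per week, taken as constant, and K the incremental CBT-I cost.

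- Full period: K + 14δ.
- Synopsis window with CBT-I cost added: K + 8δ.
- Omitted: 6δ.

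The sign of the omission is the sign of δ, which is unknown. If both arms use services at the same rate, δ = 0 and nothing is lost from the difference. If δ is not constant, the omitted amount need not be in proportion to weeks.

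**What the programme weeks contribute to QALYs (illustration).** Assume a utility difference of 0 at baseline, 0.05 post-programme, and 0.05 or 0.03 at follow-up, with linear interpolation. For a 6-week programme and 0.05 at follow-up:

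- Programme weeks: (6/52) × 0.05/2 = 0.0029.
- Follow-up weeks: (8/52) × 0.05 = 0.0077.
- Programme share: 0.0029/0.0106 = 27%.

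Across 6 to 8 weeks to the post-programme visit and both follow-up values, the programme share runs from 27% to 38%. The utility values are assumed; they show only that the choice of window is not negligible.

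**The case against.** The strongest reply is that the ICER is defined in Section 8.1, not in the synopsis. Section 8.1 values all resource use and includes the CBT-I cost, which arises before follow-up begins. The log book already records contacts in the programme weeks. Read together, these sections allow an ICER with full-period costs. The synopsis outcome also has a coherent meaning of its own: the change between two equal 8-week CSRI windows, reported beside the ICER and not as its numerator.

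Much of this stands. A reader might infer that the planned ICER does divide costs from one period by effects from another. The documents do not support that. QALYs from baseline are an inference from the EQ-5D-5L schedule, and the sections just cited point away from a numerator limited to follow-up.

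What the reply does not do is settle the period. The sentence on unit costs says how resource use is priced, not when it is counted. No section names the log book as the source for the ICER, says how it combines with the CSRI, or provides for log books that are not returned. If the synopsis outcome is a separate before-after comparison, then the plan names no cost outcome for the ICER. Restricting both costs and QALYs to follow-up does not help either: the CBT-I cost would fall outside the window, and QALYs gained during the programme would be dropped.

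**Conclusion.** The synopsis cost window conflicts with the log book in Section 5.6, with the costing in Section 8.1 and with EQ-5D-5L measured from baseline. The plan defines no common period for costs and QALYs. A mismatch follows only if the synopsis outcome supplies the ICER's healthcare costs and QALYs are counted from baseline. In that case about 6 of 14 weeks (43%; 47% to 50% if the post-programme visit falls at 7 or 8 weeks) is missing from healthcare costs but present in QALYs, provided that follow-up starts at programme end.

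The 43% is a share of time. A reader might take it as the amount by which incremental cost is understated. That would need an evenly accruing between-arm difference and would apply to healthcare cost alone, leaving out the CBT-I cost. Since the QALY window is not stated and the cost difference is unknown, neither the size nor the direction of any ICER error can be computed.

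The point concerns a secondary objective. It should be corrected, because the present text allows incompatible analyses and the correction is cheap.

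**What to change.** 1. Restate the synopsis outcome as healthcare costs from randomisation to the 8-week follow-up, plus the CBT-I cost. Say from which date the 8 weeks run.
2. State in Section 8.1 that QALYs and the ICER cover that same period, with the baseline EQ-5D-5L taken as the value at randomisation.
3. Name the log book as the main source of resource use.
4. Add the CSRI to the post-intervention mailing, with recall back to randomisation, as back-up for log books that are missing or incomplete. With the follow-up CSRI this closes the gap over the programme weeks.
5. Adjust incremental costs for baseline CSRI cost, which the trial already collects.

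The cost is protocol wording and one extra form in a mailing that is already sent. The downside is slightly more burden on participants. Items 1 to 3 remove the conflict by themselves; item 4 guards against lost log books, and item 5 uses data already in hand.
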